11. OTHER RESEARCH ACTIVITY SPECIFICATIONS

The Study Calendar - Section 3 summarizes the trial procedures to be performed at each visit.

11.1. Medical History

A medical history for each subject will be obtained by the Investigator or qualified designee. Medical history will include all active conditions, and any condition diagnosed within the prior 10 years that are considered to be clinically significant by the Investigator. Details regarding the disease for which the subject has enrolled in this study will be recorded separately and not listed as medical history.

Medical history must be graded per CTCAE v.5 to facilitate the identification of grade changes from baseline. Subjects will be asked about their medical conditions at each study visit (e.g., any new admissions or changes in existing conditions) and new medical history, if any, will be recorded throughout the study.

11.2. Prior and Concomitant Medications

Prior Medications

The Investigator or qualified designee will review prior medication use, including any protocol-specified washout requirements, and record prior medication taken by the subject within 28 days before starting the trial (time of consent). Treatment for the disease for which the subject has enrolled in this study will be recorded separately and not listed as a prior medication.

Concomitant Medications

The Investigator or qualified designee will record medication, if any, taken by the subject during the trial.

11.3. Adverse Events

The Investigator or qualified designee will assess each subject to evaluate for potential new or worsening AEs as specified in the Study Calendar in Section 3 or more frequently if clinically indicated. Please refer to Section 15 for detailed information regarding the assessment and recording and reporting of AEs.

11.4. Full Physical Exam

The Investigator or qualified designee will perform a full physical exam during the screening period. Clinically significant abnormal findings should be recorded as medical history. Full physical exam requires assessment of major organ sites (Constitutional, Head and Neck, Cardiovascular, Pulmonary, Abdominal, Musculoskeletal, Lymph, Neurological, and Skin).

11.5. Directed Physical Exam

Except for at screening, the Investigator or qualified designee will perform a directed physical exam as clinically indicated prior to trial treatment administration.

11.6. Vital Signs

The Investigator or qualified designee will take vital signs at screening, prior to the administration of each dose of trial treatment and at treatment discontinuation as specified in the Study Calendar. Vital signs should include: temperature, pulse, respiratory rate, weight and blood pressure. Height will be measured at screening only.

11.7. Eastern Cooperative Oncology Group (ECOG) Performance Scale

The Investigator or qualified designee will assess ECOG status (see Appendix 2) at screening, prior to the administration of each dose of trial treatment and discontinuation of trial treatment as specified in the Study Calendar.

11.8. Tumor Imaging and Assessment of Disease

Only the Investigator or qualified designee (MD only) may determine the assessment of disease recurrence.

Patients will undergo imaging (MRI of the liver, with contrast) at baseline and then at their 28 day post I/O safety evaluation after completion of durvalumab. If a patient has a PR or CR, confirmation scans are required no more than 4 weeks after the scan in which response was first observed.

Subjects will continue to have MRIs for standard of care every 6 months post-transplant from which their survival and disease status may be abstracted. In the event a subject does not receive a transplant they will still receive a standard of care MRI every 6 months from which survival and disease status may be abstracted.

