 - Two 10 mL EDTA tubes collected 4 weeks post-transplant +/- 3 days.
- k. Per correlative section #9. Stool sample must be collected after eligibility is confirmed but prior to I/O.
- l. tissue will be sequenced by CARIS as a SOC process.
- m. The post-I/O safety eval must occur 28 days following the final dose of durvalumab.
- n. A minimum 28-day gap after I/O before beginning L/R is required. L/R therapy can continue/repeat per treating physician discretion.
- o. At least after 72 days following final dose of durvalumab.
- p. Every 6 months +/- 1 month for standard of care, survival and disease progression data may be abstracted from this imaging.
- q. Transplant graft rejection data will be collected at 30 days after transplant and at 3 months and 6 months during long term follow-up.
- r. Subjects should be contacted by telephone or seen in clinic every 3 months from the end of I/O for the first year then every 6 months for up to 5 years to assess for survival status. Time-points noted under L/R Therapy, Transplant, and Post-op are intended to indicate that depending on the timing of each these may contain q3month time-points from I/O at which this data collection should occur.
- s. Tumor assessments must include measures for either RECIST 1.1 or mRECIST or both if institutionally allowed.
- t. 30-day post-transplant SOC visit in oncology with a +/- 7 day window to include medical history and physical.

Table of Contents

1.	Protocol Synopsis	2
2.	SCHEMA 5	
3.	STUDY CALENDAR	6
4.	abbreviations and definition of terms	10
5.	OBJECTIVES 14	
5.1.	Primary Objectives.....	14
5.2.	Secondary Objectives.....	14
5.3.	Exploratory Objectives	14
6.	BACKGROUND	14
6.1.	Immunotherapy Background	14
6.2.	Durvalumab (MEDI4736) Background	15
6.3.	Tremelimumab Background	16
6.4.	Durvalumab in combination with tremelimumab	16
6.5.	Durvalumab + tremelimumab combination therapy dose rationale.....	17
6.6.	Hepatocellular Carcinoma Background.....	18
6.7.	Correlative Studies Background	19
7.	PATIENT SELECTION: Eligibility.....	20
7.1.	Inclusion Criteria	20
7.2.	Exclusion Criteria	21
7.3.	Inclusion of Women and Minorities	23
8.	REGISTRATION PROCEDURES	23
8.1.	Assignment of Screening and Subject Numbers.....	23
8.2.	Patient Screening	24
8.3.	Patient Registration.....	24
8.4.	General Guidelines.....	24
9.	BIOMARKER, CORRELATIVE, AND SPECIAL STUDIES	25
9.1.	Biomarker Plan	25
9.2.	Exploratory/Ancillary Correlative Studies	27
10.	TREATMENT PLAN.....	28

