10.2. Durvalumab + tremelimumab combination therapy

Tremelimumab 300 mg via IV infusion x 1 dose on day 1 of the first cycle, plus durvalumab 1500 mg via IV infusion Q4W starting on day 1, for up to a maximum of 4 months (5 doses of durvalumab). N.B If a patient's weight falls to 30kg or below (≤ 30 kg), then the patient should receive weight-based dosing equivalent to 20 mg/kg of durvalumab Q4W after consultation between the investigator and study physician, until the weight improves to above 30 kg (>30 kg), at which point the patient should start receiving the fixed dosing of durvalumab 1500 mg Q4W).

Patients will be treated with the immunotherapy combination for up to 4 months. After a minimum 28 day gap following the final durvalumab dose, they will undergo locoregional therapy per institutional standards. Eventually, after a minimum 72-day gap from the end of immunotherapy, they will undergo liver transplant.

Tremelimumab will be administered first over 1 hour; the durvalumab infusion will then be started approximately 1 hour after the end of the tremelimumab infusion to allow for a 1 hour observation

period. Standard infusion time for each is 1 hour, however if there are interruptions, the total allowed time must not exceed 4 hours from the start of infusion at room temperature per infusion.

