16. MEASUREMENT OF EFFECT

16.1. **Antitumor Effect – Solid Tumors**

For the purposes of this study, patients should be re-evaluated for response 28 days after

completion of I/O +/-3 days. . In addition to a baseline scan, confirmatory scans should also be obtained (not less than 4) weeks following initial documentation of objective response.

Response and progression will be evaluated in this study using RECIST version 1.1 and/or the mRECIST guidelines (both when institutionally allowed).

Definitions

Evaluable for Toxicity. All patients will be evaluable for toxicity from the time of their first treatment with *Durvalumab*

Evaluable for Response. All patients who have received at least one cycle of therapy and have their disease re-evaluated will be considered evaluable for response (exceptions will be those who exhibit objective disease progression prior to the end of Cycle 1 who will also be considered evaluable). Patients on therapy for at least this period and who meet the other listed criteria will have their response classified according to the definitions set out below.

Evaluable Non-Target Disease Response. Patients who have lesions present at baseline that are evaluable but do not meet the definitions of measurable disease, have received at least one cycle of therapy, and have had their disease re-evaluated will be considered evaluable for non-target disease. The response assessment is based on the presence, absence, or unequivocal progression of the lesions.

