16.1.3. Response Criteria

All patients will have their best response from the start of study treatment until the end of treatment classified as outlined below.

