16.1.3.3. Evaluation of Best Overall Response

The best overall response is the best response recorded from the start of the treatment until disease

progression/recurrence (taking as reference for progressive disease the smallest measurements recorded since the treatment started). The patient's best response assignment will depend on the achievement of both measurement and confirmation criteria.

Integration of target, non-target, and new lesions into response assessment

Target Lesions	Non-Target Lesions	New Lesions	Overall Response	Best Response for This Category Also Requires
Target lesions ± non target lesions				
CR	CR	No	CR	Normalization of tumor markers, tumor nodes <10 mm & confirmation ≥ 4 wks.
CR	Non-CR/non-PD	No	PR	Normalization of tumor markers, tumor nodes <10 mm & confirmation ≥ 4 wks.
CR	Not all evaluated	No	PR	confirmation ≥ 4 wks
PR	Non-PD/not all evaluated	No	PR	confirmation ≥ 4 wks
SD	Non-PD/not all evaluated	No	SD	Documented at least once ≥4 weeks from baseline
Not all evaluated	Non-PD	No	NE	
PD	Any	Any	PD	no prior SD, PR or CR
Any	PD	Any	PD	no prior SD, PR or CR
Any	Any	Yes	PD	no prior SD, PR or CR
Non target lesions ONLY				
No Target	CR	No	CR	Normalization of tumor markers, tumor nodes <10 mm
No Target	Non-CR/non-PD	No	Non-CR/non-PD	
No Target	Not all evaluated	No	NE	
No Target	Unequivocal PD	Any	PD	
No Target	Any	Yes*	PD	

Note: Patients with a global deterioration of health status requiring discontinuation of treatment without objective evidence of disease progression at that time should be reported as "symptomatic deterioration." This is a reason for stopping therapy, but is NOT objective PD. Every effort should be made to document the objective progression even after discontinuation of treatment.
 
*Investigators should record all new lesions. If the new lesion is felt to be equivocal, treatment may be continued pending further assessments.
				

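### The radiologic response rules conflict on confirmation and on the response window, so the reported rate is not uniquely defined and can reflect locoregional therapy

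*Combined protocol and SAP*

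**What the plan says.** **Confirmation.** Section 11.8 sets an upper limit: "confirmation scans are required no more than 4 weeks after the scan in which response was first observed". Section 16.1 sets a lower limit: "confirmatory scans should also be obtained (not less than 4) weeks following initial documentation of objective response". The table in Section 16.1.3.3 repeats the lower limit, for example "tumor nodes <10 mm & confirmation ≥ 4 wks" for a complete response. Section 16.1.3.3 also makes the best-response category depend on meeting the confirmation criterion. The study calendar has no confirmation visit.

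**Response window.** Three are given.
- The synopsis and Section 14.3.1 assess radiologic response once immunotherapy is complete and before locoregional therapy starts.
- Section 16.1.3: "All patients will have their best response from the start of study treatment until the end of treatment classified as outlined below".
- Section 16.1.3.3: "The best overall response is the best response recorded from the start of the treatment until disease" progression or recurrence, with no cut-off at locoregional therapy.

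**Other treatment.** Section 10.2: "After a minimum 28 day gap following the final durvalumab dose, they will undergo locoregional therapy per institutional standards". Section 10.7 adds RECIST scans every 12 weeks, give or take 1 week, for patients who stop drug permanently without progression. These continue to progression or death and do not stop at locoregional therapy.

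**Criterion and denominator.** A calendar footnote says "Tumor assessments must include measures for either RECIST 1.1 or mRECIST or both if institutionally allowed". Section 14.3 reports response as proportions and names no denominator. Section 16.1 says "All patients who have received at least one cycle of therapy and have their disease re-evaluated will be considered evaluable for response", with an exception that keeps patients who progress during cycle 1.

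**The concern.** Radiologic response is one of the measures named for the secondary efficacy objective, and the objective is worded as the efficacy of immunotherapy. The trial has one arm, so no comparison can separate the effect of immunotherapy from that of the locoregional therapy that follows. Only the timing of the scan and the definition of response can do so, and here the definitions disagree. Two analysts who each followed the document could count different patients as responders, over different periods, by different criteria and with different denominators.

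**Working it through.** The plan gives no target rate, precision or sample size for response, so there is no figure to reproduce. The check is day arithmetic, with day 0 the last durvalumab dose.

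**Inputs**
- Post-immunotherapy MRI: day 28 ± 3, so day 25 to 31 (Sections 10.6.1, 11.8 and 16.1; study calendar).
- Confirmation interval d: at most 28 days (Section 11.8); at least 28 days with no upper limit (Sections 16.1 and 16.1.3.3).
- Earliest locoregional therapy: day 28, with no latest day (Section 10.2).
- Earliest transplant: day 72 (Section 10.2).

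**Step 1: can both confirmation rules be met?** d ≤ 28 and d ≥ 28 together give d = 28. The joint window is one day, with no tolerance stated.

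**Step 2: where does confirmation fall?** Confirmation day = MRI day + 28.

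| MRI day | Confirmation day | Days after locoregional therapy may start (minus 28) | Days before earliest transplant (72 minus) |
|---|---|---|---|
| 25 | 53 | 25 | 19 |
| 28 | 56 | 28 | 16 |
| 31 | 59 | 31 | 13 |

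These days are the latest allowed by Section 11.8 and the earliest allowed by Section 16.1.

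**Step 3: is a confirmation free of locoregional therapy possible?** Under the at-least-4-weeks rule, only if locoregional therapy starts after day 53, 56 or 59 respectively. Under Section 11.8, if locoregional therapy starts on day 28, the time left is max(0, 28 − MRI day) = 3, 0 or 0 days. Section 16.2 reports guideline advice to read mRECIST 1 month after a treatment, locoregional therapy included. If that therapy starts near day 28, the confirmation scan falls at about that time.

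**Step 4: windows side by side.**
- Section 14.3.1 contains the post-immunotherapy MRI and nothing after locoregional therapy.
- Section 16.1.3 ends at a point the protocol does not define. If it means the last immunotherapy dose, the window contains no scheduled scan after baseline.
- Section 16.1.3.3 takes in any scan after locoregional therapy until progression. If the 12-weekly scans of Section 10.7 are counted from the last dose (an assumption; no starting point is given), the first falls at 84 ± 7, or day 77 to 91, well after day 28.

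**Step 5: direction and possible size. All rates here are assumed.**
- *Section 14.3.1 window with confirmation.* A second scan can only keep or remove a responder, so the confirmed rate cannot exceed the unconfirmed one. Holding to exactly 28 days would lose true responders.
- *Section 16.1.3.3 window.* Let r be the true response to immunotherapy and q the share of non-responders later scored as responders because of locoregional therapy. Reported rate = r + (1 − r)q. With r = 0.10 and q = 0.30: 0.10 + 0.90 × 0.30 = 0.37. With r = 0.30 and q = 0.50: 0.30 + 0.70 × 0.50 = 0.65.
- *Denominator.* Seven responders are 7/30 = 23.3% of 30 treated patients, but 7/25 = 28.0% if 5 were never re-scanned and are left out.

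**The case against.** The strongest reply is that the plan already settles the time point. The synopsis and Section 14.3.1 both place radiologic response before locoregional therapy. The calendar marks tumor assessments only at screening and at the post-immunotherapy evaluation, and Section 10.6.1 puts that visit before any new anti-cancer treatment. On this view Section 16 is generic RECIST text. Much of this stands: if Section 14.3.1 governs, a first response cannot come from locoregional therapy. But nothing gives it precedence. Section 16.1 says how response is evaluated in this study, and Section 16.1.3.3 makes confirmation a condition of the category. The clash over confirmation remains on any reading.

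Three further replies also stand. The 28 days before locoregional therapy is a minimum, so a clean confirmation scan is possible, and the documents do not say how often it would occur. Upward bias is not shown in general; it follows from the Section 16.1.3.3 window or from a denominator of re-scanned patients only. And no section says that RECIST 1.1 and mRECIST results are to be pooled, though none says they are to be kept apart.

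A reader might go further and infer that the transplant itself could be scored as a complete response, because the lesions leave with the liver. With 20 transplants among 30 patients that would be 20/30 = 67%, even if immunotherapy did nothing. The documents do not support this. Section 11.8 uses the post-transplant MRIs to update survival and disease status; no section directs that they be scored for response. The Section 11.8 limit on confirmation ends by day 59, before the earliest transplant on day 72. Section 16.1.3.3 does not exclude such scans, which is a reason to close the gap but not evidence that the plan intends it.

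**Conclusion.** The point holds as a defect of definition in a secondary efficacy endpoint, and it should be fixed. Two facts rest on the text alone: the confirmation rules agree on a single day only, and the three response windows are incompatible. That confirmation can reflect locoregional therapy follows from the protocol's own days: confirmation at 4 weeks or more comes no earlier than day 53 to 59, against locoregional therapy from day 28. How many patients this would affect depends on when locoregional therapy actually starts, which the documents do not give. The sign of the bias depends on the reading: strict confirmation can lower the rate, while the Section 16.1.3.3 window or a re-scanned-only denominator can raise it. The 37% to 65% range and the 23.3% versus 28.0% contrast are illustrations under assumed rates, not forecasts. The primary safety endpoint, its power and the interim safety rules do not depend on response and are unaffected.

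**What to change.** Reconcile Sections 10.7, 11.8, 14.3.1, 16.1, 16.1.3 and 16.1.3.3 to the time point already in Section 14.3.1:

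- **Main definition.** Radiologic response is the category at the post-immunotherapy MRI taken before any locoregional therapy, and it is labelled unconfirmed. Scans after locoregional therapy or transplant, including those under Section 10.7, do not count toward it.
- **Confirmation.** State one interval throughout. Report any confirmed rate separately, using only confirmation scans taken before locoregional therapy.
- **Criterion.** Report RECIST 1.1 and mRECIST as two rates from the same MRI, never pooled. RECIST 1.1 can be required for everyone because Section 7.1 makes a RECIST 1.1 target lesion an entry criterion.
- **Denominator.** Use all treated patients. A patient with no scan before locoregional therapy counts as a non-responder.

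The cost is mostly wording. There are two real downsides. The main rate is unconfirmed, and it is never lower than a confirmed rate from the same scans. Sites that planned mRECIST only must also record RECIST 1.1, so the proviso about what institutions allow has to be resolved with them. No change to the timing of treatment or transplant is proposed.

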11.9. Laboratory Safety Evaluations (Hematology, Chemistry and Other)

Laboratory tests for hematology, chemistry, and others are specified in Table 5

Table 5. Laboratory Tests

Hematology	Chemistry	Other
Hemoglobin	Albumin	Serum β -human chorionic gonadotropin \dagger
Platelet count	Alkaline phosphatase	(β -hCG) \dagger
WBC (total and differential)	Alanine aminotransferase (ALT)	Total triiodothyronine (T3) ^a
Red Blood Cell Count	Aspartate aminotransferase (AST)	Free thyroxine (T4) ^a
Absolute Neutrophil Count	CO ₂ or bicarbonate	Thyroid stimulating hormone (TSH)
Absolute Lymphocyte Count	Calcium	Prothrombin time PT/INR
	Chloride	Partial Thromboplastin Time (PTT)
	Glucose	Amylase
	Phosphorus	Lipase
	Potassium	Alpha Fetoprotein (AFP)
	Sodium	
	Creatinine	
	Magnesium	
	Total Bilirubin ^b	
	Direct Bilirubin	
	Total protein	

	Blood Urea Nitrogen	

† Done on all women of child-bearing potential
 
 a. Free T3 or free T4 will only be measured if TSH is abnormal or if there is a clinical suspicion of an AE related to the endocrine system. b. If total bilirubin is $\geq 2 \times$ ULN (and no evidence of Gilbert's syndrome), then fractionate into direct and indirect bilirubin. 		

12. DOSING DELAYS/MODIFICATIONS & TOXICITY MANAGEMENT

12.1. Durvalumab and tremelimumab

Guidelines for the management of immune-mediated reactions, infusion-related reactions, and non-immune-mediated reactions for durvalumab are provided in the durvalumab/tremelimumab Toxicity Management Guidelines (TMGs) in Appendix 1.

Patients should be thoroughly evaluated, and appropriate efforts should be made to rule out neoplastic, infectious, metabolic, toxin, or other etiologic causes of the imAE. Serologic, immunologic, and histologic (biopsy) data, as appropriate, should be used to support an imAE diagnosis. In the absence of a clear alternative etiology, events should be considered potentially immune related.

In addition, there are certain circumstances in which durvalumab and tremelimumab should be permanently discontinued (see Section 10.7 Discontinuation of Active Treatment of this protocol and the Dosing Modification and Toxicity Management Guidelines in Appendix 1).

Following the first dose of IP, subsequent administration of durvalumab and tremelimumab can be modified based on toxicities observed as described in the Dosing Modification and Toxicity Management Guidelines in Appendix 1. These guidelines have been prepared to assist the Investigator in the exercise of his/her clinical judgment in treating these types of toxicities. These guidelines apply to AEs considered causally related to durvalumab monotherapy and the durvalumab + tremelimumab regimen by the reporting investigator.

Dose reductions are not permitted. In case of doubt, the treating physician should consult with the UC PI.

Patients will be monitored during and after the infusion with assessment of vital signs at the times specified in the study calendar.

1. In the event of a \leq Grade 2 infusion-related reaction, the infusion rate of study drug may be decreased by 50% or interrupted until resolution of the event and re-initiated at 50% of the initial rate until completion of the infusion.
2. For patients with a \leq Grade 2 infusion related reaction, subsequent infusions may be administered at 50% of the initial rate. Acetaminophen and/or an antihistamine (e.g., diphenhydramine) or equivalent medications per institutional standard may be administered at the discretion of the investigator.
3. If the infusion related reaction is \geq Grade 3 or higher in severity, study drug will be discontinued. Standard infusion time is one hour, however if there are interruptions, the total allowed time must not exceed 8 hours at room temperature (otherwise requires new infusion preparation). For management of patients who experience an infusion reaction, please refer to the toxicity and management guidelines in [Error! Reference source not found.](#)

As with any antibody, allergic reactions to dose administration are possible. Appropriate drugs and medical equipment to treat acute anaphylactic reactions must be immediately available, and study personnel must be trained to recognize and treat anaphylaxis. The study site must have immediate access to emergency resuscitation teams and equipment in addition to the ability to admit patients to an intensive care unit if necessary.

